### **5.13.7. Analyses of MRI Data**

Magnetic resonance imaging findings believed to have potential clinical significance will be reported to the investigator and sponsor. Any new or aggravated clinically relevant abnormal MRI finding as compared with the baseline MRI should be reported to Lilly or its designee as an AE. If a clinically meaningful change in MRI is noted during the study, an additional, full neurological exam will be performed as soon as possible, along with any other medical follow-up deemed necessary by the investigator.

To evaluate any changes in MRI data following treatment, Pearson's chi-square tests will be used to compare frequencies of responses in the MRI parameters.

Frequencies and percentages of the following amyloid-related imaging abnormality – edema (ARIA-E, also known as vasogenic edema) and ARIA – hemorrhage (ARIA-H, also known as microhemorrhage) parameters will be summarized:

- ARIA-E:
  - Severity (mild, moderate, severe, or no presence)
  - Status compared to the previous MRI(s) (increased, unchanged, partial resolution, or complete resolution)
- ARIA-H:
  - Number of ARIA-H (1, 2 to 5, 6 to 10, >10, or no presence),
  - Baseline to endpoint changes (increase in size of pre-existing ARIA-H, increase in number of ARIA-H, no change, partial resolution, or complete resolution)

A listing of abnormal MRI finding will also be presented by subject and visit.

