5.1. Overall Design

Study LLCF is a multicenter, randomized, double-blind, placebo-controlled study in patients with mild AD dementia. This study (Study LLCF) will enroll patients with mild AD dementia using National Institute on Aging-Alzheimer's Association (NIA-AA) work group consensus guidelines (McKhann et al. 2011) with amyloid deposition confirmed by florbetapir F 18 PET imaging. The treatment phase will be 52 weeks.

Figure LLCF.1 illustrates the study design.

Abbreviations: AD = Alzheimer's disease; FP = follow-up period; LY = LY3202626.

Note: This is a multicenter, randomized, parallel-group, 52-week-long double-blind, placebo-controlled, study of 2 fixed dose levels of LY3202626 (3 mg and 12 mg) in patients with mild AD dementia and evidence of amyloid pathology.

Approximately 380 mild AD dementia patients will be enrolled (approximately 167 in the placebo and 12 mg groups, and approximately 45 in the 3 mg group).

Figure LLCF.1. Illustration of study design for Clinical Protocol I7X-MC-LLCF.

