5.2. Number of Participants

Approximately 1000 participants will be screened to achieve approximately 380 randomized and approximately 320 completed evaluable participants, assuming approximately 15% drop out.

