10.3. Statistical Analyses

10.3.1. General Statistical Considerations

Statistical analysis of this study will be the responsibility of Eli Lilly and Company.

Unless otherwise specified, all safety analyses will be conducted on the safety population and all efficacy and PD analyses will be conducted on the efficacy population as defined above (Table LLCF.3).

No adjustments will be made for multiple comparisons.

All total and subscale scores will be derived from individual items. If any individual item is missing, the corresponding total and subscale scores will be considered missing, except for the ADAS-Cog₁₃, which will be imputed. The imputation algorithm will be specified in the statistical analysis plan (SAP).

All tests of treatment effects of biological efficacy or clinical efficacy will be conducted at a 1-sided α =.10, unless otherwise stated. Safety assessments will be conducted at a 2-sided α =.05.

A repeated measures analysis refers to a restricted maximum likelihood (REML)-based, mixed effects repeated measures analysis using all the longitudinal observations at each post-baseline

visit. A repeated measures analysis model will include the fixed, categorical effects of treatment group, visit, and treatment-by-visit interaction, as well as the continuous, fixed covariates of baseline and the baseline-by-visit interaction, unless otherwise noted. Unless otherwise specified, when an ANOVA model is used to analyze a continuous efficacy variable, the model will contain the main effects of treatment. Similar logic is applied to an ANCOVA model, which in general, refers to the ANOVA model with baseline value added as a covariate. Type III sum-of-squares for the least squares (LS) LS Means will be used for statistical comparisons using an ANOVA or ANCOVA. Categorical comparisons between treatment groups will be performed using Fisher's exact tests, where appropriate.

Any change to the data analysis methods described in the protocol will require an amendment to the protocol only if it changes a principal feature of the protocol. Any other change to the data analysis methods described in the protocol, and the justification for making the change, will be described in the clinical study report (CSR). Additional exploratory analyses of the data will be conducted as deemed appropriate.

SAS® software will be used to perform most or all statistical analyses.

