## 5. A Priori Statistical Methods

### 5.1. General Considerations

All tests of treatment effects of biological efficacy or clinical efficacy will be conducted at a 1-sided  $\alpha=.10$ , unless otherwise stated. Safety assessments will be conducted at a 2-sided  $\alpha=.05$ .

A repeated measures analysis refers to a restricted maximum likelihood (REML)-based, mixed effects repeated measures analysis using all the longitudinal observations at each post-baseline visit.

All analyses will follow the intent-to-treat (ITT) principle unless otherwise specified. An ITT analysis is an analysis of data by the groups to which subjects are assigned by random allocation, even if the subject does not take the assigned treatment, does not receive the correct treatment, or otherwise does not follow the protocol.

When change from baseline is assessed, subjects will be included in the analysis only if both a baseline and a postbaseline measure are available. Unless otherwise defined, Visit 3 is the baseline visit, and baseline value is defined as last value available before or at Visit 3.

All total and subscale scores will be derived from individual items. If any individual item is missing, the corresponding total and subscale scores will be considered missing, except for the ADAS-Cog13 and ADCS-iADL, which will be imputed.

A repeated measures analysis model will include the fixed, categorical effects of treatment, visit, and treatment-by-visit interaction, as well as the continuous, fixed covariates of baseline, baseline-by-visit interaction, and age at baseline.

When an analysis of covariance (ANCOVA) model is used to analyze a continuous efficacy variable, the model will contain the main effects of treatment with baseline value and age at baseline added as covariates. For ANCOVA analysis on change from baseline to Week 52 endpoint, change from baseline to last observation during treatment period will be used if patients do not have Week 52 observation available.

Categorical comparisons between treatment groups will be performed using Fisher's exact tests or logistic regression where appropriate.

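### SAP 5.13.7 uses Pearson's chi-square for the ARIA tables with no exact fallback, so individual p-values are unreliable if ARIA is uncommon (minor)

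*SAP*

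**What the plan says.** SAP 5.13.7 (Analyses of MRI Data) states that Pearson's "chi-square tests will be used to compare frequencies of responses in the MRI parameters". It then lists the ARIA items to be summarised. ARIA-E severity has four levels including absence, and the number of ARIA-H has five: "Number of ARIA-H (1, 2 to 5, 6 to 10, >10, or no presence"). There are also items for change in status. The section gives no minimum expected count and no exact alternative. It does not say whether the test is run across all three arms or for each dose against placebo.

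The general rule differs. SAP 5.1 calls for Fisher's "exact tests or logistic regression where appropriate". Protocol 10.3.1 also names Fisher's exact test, qualified by where it is appropriate. Fisher's test is named for adverse events (SAP 5.13.2 and 5.13.3), treatment-emergent laboratory values (5.13.4), vital signs (5.13.5), ECGs (5.13.6) and eye findings (5.13.8.3).

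Protocol 5.1 plans "approximately 167 in the placebo and 12 mg groups, and approximately 45 in the 3 mg group". Safety is tested at a two-sided 0.05 with no multiplicity adjustment. Protocol 10.3.4 describes safety comparisons as dose groups against placebo.

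**The concern.** Pearson's test takes its p-value from a large-sample distribution that is accurate when expected counts are not small. Here several response levels are spread over three arms, one of them about a quarter the size of the others. If few patients have ARIA, most non-null cells have expected counts below 1.

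ARIA is a named MRI safety endpoint, and its p-values are read at 0.05 without adjustment. A table with one or two cases in the small arm could then carry a p-value that overstates the evidence several-fold. The SAP already uses a method for sparse binary safety data that avoids this, and it gives no reason for treating ARIA differently.

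**Working it through.** **Inputs.** Arm sizes 167/167/45 (protocol 5.1), total 379. Safety alpha 0.05, two-sided (SAP 5.1). The documents give no ARIA rate, so the case counts below are assumptions.

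**The plan's own sizes.** Protocol 5.2 has "approximately 380 randomized and approximately 320 completed evaluable participants, assuming approximately 15% drop out". Check: 320/0.85 = 376.5, or 377; 380 × 0.85 = 323; 167 + 167 + 45 = 379. The stated figures agree with one another.

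**How many cases would avoid sparse cells.** The expected count in 3 mg is K × 45/379 for K cases in one category. Setting this to 5 gives K = 5 × 379/45 = 42.1, so about 43 cases in a single category, or roughly 11% of patients.

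**One case in 3 mg, none elsewhere, three-arm test.** Empty response levels drop out, leaving a 3 × 2 table. Expected case counts are 167/379 = 0.441, 0.441 and 45/379 = 0.119.

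- Pearson: for a single case in an arm of size n out of N, X² = (N/n − 1) × N/(N − 1) = (379/45 − 1) × 379/378 = 7.44. With df 2, p = 0.024.
- Exact: under the null the case falls in 3 mg with probability 45/379 = 0.119. The other two placements are each more probable (167/379), so the exact p is 0.119.

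The same calculation for other tables:

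| Comparison | Arm sizes | Cases | Pearson p | Exact p |
|---|---|---|---|---|
| Three-arm | 167/167/45 | 0/0/1 | 0.024 | 0.119 |
| Three-arm | 167/167/45 | 0/0/2 | 0.0006 | 0.014 |
| Three-arm | 142/142/38 (15% dropout) | 0/0/1 | 0.024 | 0.118 |
| Three-arm | 150/150/45 | 0/0/1 | 0.035 | 0.130 |
| Three-arm | 130/130/45 | 0/0/1 | 0.055 | 0.148 |
| Three-arm | 100/100/45 | 0/0/1 | 0.107 | 0.184 |
| 3 mg vs placebo | 45 vs 167 | 1 vs 0 | 0.053 | 0.212 |
| 3 mg vs placebo | 45 vs 167 | 2 vs 0 | 0.006 | 0.044 |
| 3 mg vs placebo | 45 vs 167 | 3 vs 2 | 0.032 | 0.065 |

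**Where the one-case result stops crossing 0.05.** The df 2 critical value is 5.99. The formula for X² shows that N must be about 7 times the 3 mg arm; the planned ratio is 379/45 = 8.4. With 45 in 3 mg, 7 × 45 = 315, which leaves about 135 in each larger arm. Below that, one case no longer gives Pearson p < 0.05.

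**Average error.** Given exactly one case overall, Pearson rejects only when that case is in 3 mg, which has probability 11.9%. Averaged over all outcomes at planned sizes, the simulated type I error of the three-arm test is 3.2% to 4.9% for common rates of 0.1% to 3%. For 3 mg against placebo it is 0.5% to 4.1% for rates of 0.3% to 4%. There is no general inflation.

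**The case against.** Several objections have force.

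- **The three-arm test is not specified.** Protocol 10.3.4 speaks of dose groups against placebo. Read that way, one 3 mg case gives 0.053 and two cases are significant under both tests. Of the pairwise examples shown, only 3/45 against 2/167 changes sides. This stands, and it is why the fix asks for the comparison to be stated.
- **Planned sizes will not be met.** The SAP's revision history says that early termination leaves most patients without a Week 52 observation. The schedule's footnotes allow an early-discontinuation MRI only after at least 24 weeks. The 3 mg arm was filled in the 1:1:1 stage, so the larger arms may lose more scans. The MRI denominators are not given. This also stands.
- **Sparsity is assumed.** No ARIA rate appears, and the ARIA-H items include pre-existing lesions, so ARIA-H may be less sparse than ARIA-E.
- **Chi-square is used elsewhere.** BMI categories use Pearson (SAP 5.13.5) and urinalysis shifts a likelihood-ratio chi-square (5.13.4). A reader might infer that ARIA is the only categorical safety table without Fisher's test; it is not.
- **Other routes exist.** Clinically relevant new or worsened MRI findings are reported as adverse events, which are compared by Fisher's test, and abnormal findings are listed by subject. That limits the harm but does not correct the p-value in the ARIA table.
- **The exact test is not always more cautious.** With 0/3/2 cases at 167/167/45, Pearson gives 0.052 and the exact test 0.037.

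Two stronger readings are tempting. One is that any single 3 mg case would be reported as a significant difference. That needs a three-arm test, arms near planned size and no case elsewhere. The other is that the plan inflates false positives overall. The average error rates do not support that.

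**Conclusion.** The point holds as a minor one. SAP 5.13.7 departs from the SAP's general rule and sets no limit on small counts. If ARIA is uncommon, individual Pearson p-values in these tables are unreliable. At planned sizes, the three-arm value is about 5 times too small with one 3 mg case (0.119/0.024) and about 24 times too small with two (0.0138/0.00057). Only the first of these changes the result at 0.05.

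This rests on three assumptions: few ARIA cases, a three-arm test for the largest discrepancies, and arm sizes near plan for the one-case crossing of 0.05. No decision rule in the documents depends on these p-values.

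**What to change.** In SAP 5.13.7, replace Pearson's chi-square with Fisher's exact test (the Fisher-Freeman-Halton form for more than two arms or levels) for the ARIA-E and ARIA-H tables. In the same sentence, state whether the comparison is across three arms or each dose against placebo, in line with protocol 10.3.4.

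The cost is one phrase in the SAP and an exact option in the program. The exact test is slightly conservative, so it gives up a little sensitivity to a real difference in a safety table.

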### **5.13.8. Additional Safety Concerns**

#### **5.13.8.1. Columbia Suicide Severity Rating Scale**

Suicidal ideation, suicidal behavior, and self-injurious behavior without suicidal intent, based on the C-SSRS, will be listed by subject and visit. Only subjects that show suicidal ideation/behavior or self-injurious behavior without suicidal intent will be displayed (i.e., if a subject answers are all 'no' for the C-SSRS, then that subject will not be displayed). However, if a subject reported any suicidal ideation/ behavior or self-injurious behavior without suicidal intent at any time point then all their ideation and behavior will be displayed, even if not positive.

In addition, the number and percent of patients who experienced at least one of various comparative measures during treatment will be presented and compared. These include treatment-emergent suicidal ideation compared to recent history, treatment-emergent serious suicidal ideation compared to recent history, emergence of serious suicidal ideation compared to recent history, improvement in suicidal ideation at endpoint compared to baseline, and emergence of suicidal behavior compared to all prior history.

#### **5.13.8.2. Skin Examination**

Skin color will be reported at baseline by using Fitzpatrick Scale Rating. The frequencies of the outcomes (I, II, III, IV, V, and VI) will be displayed by treatment group.

Any hypopigmentation will be assessed by location, percentage of body surface area involvement (BSA), degree (partial/decreased pigmentation to complete depigmentation), and other findings in or around the hypopigmentation area (e.g., redness or induration). A static physician's global assessment (sPGA) will be used to determine the subject's overall hypopigmentation severity at a given timepoint using a visual analog scale (VAS) ranging from 0 to 100. In addition, subjects noted to have evidence of hypopigmentation will be asked to record how bothersome they find the hypopigmentation on a VAS ranging from 0 to 100.

Frequency tables and summary statistics for the continuous parameters will be given by treatment group.

In order to display any changes/deteriorations during treatment, the following will be reported: number of subjects for whom no hypopigmentation was observed at baseline, but for whom at least once after randomization hypopigmentation was observed during treatment period; summary statistics for the difference of maximum value during treatment minus baseline value for percentage BSA of hypopigmentation, overall severity (sPGA) and "how bothered is the subject"; shift table of baseline vs. maximum value during treatment for degree of overall lesion severity.

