6.2. Exclusion Criteria

Patients will be excluded from study enrollment if they meet any of the following criteria at screening:

Medical Conditions

- [8] Lack, in the investigator's opinion, of adequate premorbid literacy, adequate vision, or adequate hearing to complete the required psychometric tests.
- [9] Significant neurological disease affecting the CNS, other than AD, that may affect cognition or ability to complete the study, including but not limited to, other dementias, serious infection of the brain, Parkinson's disease, multiple concussions, or epilepsy or recurrent seizures (except febrile childhood seizures)
- [10] Current serious or unstable illnesses including retinal, cardiovascular (including unstable ischemic cardiovascular disease), hepatic, renal, gastroenterologic, respiratory, endocrinologic, neurologic (other than AD), psychiatric, immunologic, or hematologic disease and other conditions that, in the investigator's opinion, could interfere with the analyses in this study; or has a life expectancy of <12 months.
- [11] History of cancer within the last 5 years, with the exception of non-metastatic basal and/or squamous cell carcinoma of the skin, in situ cervical cancer, non-progressive prostate cancer, or other cancers with low risk of recurrence or spread.

- [12] Patients with any current primary psychiatric diagnosis other than AD if, in the judgment of the investigator, the psychiatric disorder or symptom is likely to confound interpretation of drug effect, affect cognitive assessment, or affect the patient's ability to complete the study. Patients with history of schizophrenia or other chronic psychosis are excluded.
- [13] Is clinically judged by the investigator to be at serious risk for suicide as assessed by medical history, examination, or the C-SSRS.
- [14] Ocular pathology that significantly limits ability to reliably evaluate vision or the retina.
- [15] History of alcohol or drug use disorder (except tobacco use disorder) within 2 years before the screening visit.
- [16] Congenital QT prolongation.
- [17] Intermittent second- or third-degree atrioventricular (AV) heart block or AV dissociation or history of ventricular tachycardia.
- [18] Has a cardiac pacemaker.
- [19] History of vitiligo and/or current evidence of post-inflammatory hypopigmentation
- [20] Severe drug allergy to 2 or more drugs classes

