9.4.5.3. Skin Examination

A complete skin examination will be performed at the times shown in the Schedule of Activities (Section 2), preferably by the same dermatologist for each patient's visit. All skin examinations must be performed by a dermatologist who will inspect the patient's unclothed full body using a ultraviolet (UV) light. The initial examination will include Fitzpatrick skin-type classification scale.

At each examination, abnormal hypopigmentation will be assessed by location, percentage of body surface area involvement, degree (partial/decreased pigmentation to complete depigmentation), and other findings in or around the hypopigmented area (such as redness or induration). A static physician's global assessment (sPGA) will be used to determine the patient's overall hypopigmentation severity at a given time point using a visual analog scale (VAS) ranging from 0 to 100. In addition, patients noted to have evidence of hypopigmentation will be asked to record how bothersome they find the hypopigmentation on a VAS ranging from 0 to 100. Skin photographs may be taken as appropriate for generating supporting documentation, but not for the purpose of primary clinical dermatologic evaluation or for data generation or analysis. A punch biopsy may be obtained at the discretion of the dermatologist.

Any clinically significant findings that result in a diagnosis should be reported to Lilly or its designee as a pre-existing condition or AE via eCRF per Section 9.2. The principal investigator will make all final determinations of AEs in consultation with the dermatologist.

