### **5.6. Population for Analysis**

The Efficacy population is defined as all randomized participants who take at least 1 dose of double-blind study treatment and have at least 1 postdose efficacy measurement, which is used to assess the effectiveness of the study drug regimen; all observed data will be included (including data gathered after a subject discontinues study drug).

In order to assess the study drug treatment effect, data gathered after a subject discontinues study drug will not be included in the analysis of per protocol population.

Additionally, when change from baseline is assessed, subjects will be included in the analysis only if both a baseline and at least 1 valid post-baseline measure are available.

All subjects who received at least 1 dose of randomized study treatment (LY3202626 or placebo) will be included in the safety analysis set. If an LY3202626 dose group is dropped following an interim analysis, subjects switched to the remaining LY3202626 dose and remaining on treatment will be accounted for as a separate group.

For the Lumbar Puncture addendum, the analysis sets will include all those subjects whose eligibility was determined by the respective biomarker, who signed consent for addendum, and who have a baseline and at least 1 valid post-baseline cerebrospinal fluid (CSF) assessment.

The PK analysis set is defined as all subjects in the safety population who have at least 1 post-dose PK assessment. The population PK analyses will be performed using this analysis set.

The primary and secondary efficacy measures will be analyzed using the efficacy population unless otherwise specified. In addition, the primary measure will be analyzed using per-protocol populations to verify the robustness of the results. Summaries and analyses for safety measures will be based on the safety population.

[Table LLCF.SAP.1](#) below defines each of the analysis populations used in this study.

[Table LLCF.SAP.2](#) lists the study measures that will be summarized and/or analyzed for each population.

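### The planned change in the hypopigmentation bother score leaves out every new case, and the SAP does not say how clear skin is coded for % BSA and sPGA

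*SAP*

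**What the plan says.** SAP 5.13.8.2 lists outputs meant to show deterioration of the skin during treatment. One is "summary statistics for the difference of maximum value during treatment minus baseline value for percentage BSA of hypopigmentation, overall severity (sPGA) and" the patient's bother score.

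The two documents restrict who gives that score in matching terms. Protocol 9.4.5.3: "patients noted to have evidence of hypopigmentation will be asked to record how bothersome they find the hypopigmentation on a VAS". SAP 5.13.8.2: "subjects noted to have evidence of hypopigmentation will be asked to record how bothersome they find the hypopigmentation on a VAS".

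The physician's score carries no such limit. Protocol 9.4.5.3: "A static physician's global assessment (sPGA) will be used to determine the patient's overall hypopigmentation severity at a given time point". The protocol also has hypopigmentation, including % BSA, assessed at every skin examination.

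The inclusion rule appears twice. SAP 5.1: "When change from baseline is assessed, subjects will be included in the analysis only if both a baseline and a postbaseline measure are available". SAP 5.6: "subjects will be included in the analysis only if both a baseline and at least 1 valid post-baseline measure are available".

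Exclusion criterion [19] in Protocol 6.2 keeps out patients with "History of vitiligo and/or current evidence of post-inflammatory hypopigmentation".

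SAP 5.13.8.2 also plans a count of patients clear at baseline who later show hypopigmentation, a shift table for lesion severity, and by-arm summaries of the continuous skin parameters.

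**The concern.** The bother score exists only where there is a lesion, while the change analysis requires a value from before treatment. A patient whose first lesion appears on treatment cannot meet both conditions. The change table would then describe only patients who already had lesions at entry, the opposite of what a table of on-treatment deterioration is for.

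Hypopigmentation is a deliberate safety focus here. There are full-body dermatologist examinations under UV light, an entry exclusion, a ban on depigmenting agents (Protocol 7.7), and hypopigmentation and pigmentation-change terms among the adverse events of special interest (SAP Table LLCF.SAP.3). A bother-change row showing little movement in every arm could be read as reassurance about a drug effect it cannot register.

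**Working it through.** The plan gives no figure that depends on this point, so there is nothing to reproduce. The check sets the collection rule for each measure against the inclusion rule, then counts patients under assumed rates.

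**Step 1. Is there a baseline value for a patient with clear skin?** SAP 5.1 takes as baseline the last value at or before Visit 3. The only skin examination by then is at Visit 1 (Protocol Section 2).

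| Measure | Who is scored | Clear skin at Visit 1 | New case in the change summary? |
|---|---|---|---|
| Bother VAS | Only patients with hypopigmentation | Not asked, so no value | No |
| sPGA | The patient, no stated limit | 0 or missing, not stated | Yes if 0, no if missing |
| % BSA | Assessed at each examination | 0 or missing, not stated | Yes if 0, no if missing |

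**Step 2. Does another rule supply the missing baseline?** SAP 5.3.2 imputes only missing items of ADAS-Cog13 and ADCS-iADL. Nothing assigns 0 to clear skin on any skin measure.

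**Step 3. Counts for the bother VAS.** N = 167 is the planned size of the 12 mg arm (Protocol 5.1). The documents give no lesion rates, so all rates here are assumptions: baseline prevalence b from 0 to 10%, and new-case rate i from 2 to 10% of patients clear at baseline.

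- Pre-existing cases = 167 × b, rounded: 0 to 17.
- New cases = (167 − pre-existing) × i, rounded: 3 to 17.
- As written: 0 to 17 patients contribute a bother change, including 0 of the 3 to 17 new cases.
- With clear skin set to 0 and all patients examined at baseline and afterwards: 167 contribute, including all 3 to 17 new cases.

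**Step 4. Effect on the mean, one assumed scenario.** Take 5% of the arm with pre-existing lesions and 6% as new cases. Let new cases average 30 on the VAS and pre-existing cases change by 0.

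- Pre-existing: 0.05 × 167 = 8.4. New: 0.06 × 167 = 10.0. Affected: 18.4.
- As written: only the 8.4 pre-existing cases contribute, so the mean change is 0.
- Clear skin = 0, all patients: (10.0 × 30) / 167 = 1.8, with a median of 0.
- Clear skin = 0, affected patients only: (8.4 × 0 + 10.0 × 30) / 18.4 = 16.3.

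**The case against.** The strongest reply is that this touches one descriptive measure and that the rest of the skin analysis is intact. Much of that stands.

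A reader might infer that all three skin change measures lose every new case. The documents do not support this. The restriction to affected patients is attached to the bother VAS alone. The sPGA is a patient-level score from 0 to 100 and % BSA has a natural zero, so both may well be recorded as 0 for clear skin. What is left for those two is an undefined coding rule.

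A reader might also infer that the plan hides a skin effect of the drug. It does not. New cases are counted directly, observed scores in the by-arm summaries need no baseline, a severity shift table is planned, and clinically significant diagnoses are reported as adverse events, with pigmentation terms compared between arms by Fisher's exact test (SAP 5.13.3). But the count gives incidence without burden, the shift table concerns severity and not bother, and nothing says the by-arm summaries will separate new from pre-existing lesions.

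Two further replies are fair. No hypothesis test is specified for these skin summaries. And if criterion [19] leaves few patients with baseline lesions, the bother-change row will rest on so few that its weakness may be visible. That lowers the risk of misreading but does not make the row informative.

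Finally, scoring bother as 0 for someone who was never asked is a convention, not an observation. That is correct, and it is why the observed values in new cases should be shown as well.

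**Conclusion.** The point holds for the bother VAS. Its planned change summary excludes 100% of patients who are clear at baseline and develop hypopigmentation. This follows from the collection and inclusion rules together and does not depend on any assumed rate. For % BSA and sPGA the same loss is possible but not established, because neither document says whether clear skin is 0 or missing.

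The size in VAS units cannot be taken from the documents. The figures of 0 against about 1.8 (all patients) or about 16 (affected patients) rest on assumed rates, an assumed score of 30 and the planned arm size. Early termination, noted in SAP Section 3, may make the real counts smaller.

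The defect should be corrected because the table cannot do what it is there for. Its reach is limited to descriptive safety reporting.

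**What to change.** In SAP 5.13.8.2, add a derivation rule: a skin examination that records no hypopigmentation, at baseline or later, counts as 0 for % BSA, sPGA and the bother VAS when maximum minus baseline is computed. Compute the change in all safety-population patients with a baseline and at least one post-baseline skin examination. Beside it, show the observed maximum on-treatment values of all three measures for patients with new hypopigmentation. That second summary uses no assigned bother scores.

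The cost is a short SAP addition and one derivation, with no new data. Any departure from the protocol's analysis methods that is not a principal feature can be described and justified in the clinical study report under SAP 5.1.

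There are two downsides. The bother value of 0 is a convention for patients who were not asked, so it should be labelled as derived. And most changes will be 0, so the all-patient mean will be small and the median probably 0. The overall summary should therefore not be shown without the one for affected patients.
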